1.0 Objectives

1.1 Describe the purpose, specific aims, or objectives of this research.

Response: The purpose of this study are to determine the effectiveness of the daily report card (DRC) approach to supporting children with ADHD in special education in schools compared to a business as usual condition. Children in the study will be randomly assigned (like flipping a coin) to business as usual, or to treatments that increases, if needed, across the school year. All children will have progress carefully monitored across the school year.

The objective is to observe whether the addition of the DRC approach is superior to special education procedures as usual .

1.2 State the hypotheses to be tested, if applicable.

NOTE: A hypothesis is a specific, testable prediction about what you expect to happen in your study that corresponds with your above listed objectives.

Response:

Aim 1. Investigate the efficacy of using a DRC mechanism to link the child with ADHD's IEP to daily classroom behavior.

Hypothesis 1. Children who have a DRC linked directly to their IEP goals and objectives will exhibit better classroom behavior and exhibit better academic productivity outcomes than children who receive school as usual (SAU) in which an IEP has been developed but has not been enhanced through use of a DRC. Children who have a DRC will also demonstrate better outcomes on measures of IEP goal attainment, school functioning, and academic progress.

Aim 2. Investigate moderators of treatment outcome.

Hypothesis 1. It is hypothesized that grade level will moderate intervention effects. It is hypothesized the DRC intervention will be more effective in the primary grades (i.e., K-3) relative to intermediate grades (i.e., 4-6) as the less complex class schedule and academic demands (e.g., fewer long-term assignments; fewer organizational demands on the student) will facilitate greater adherence and implementation and therefore better outcome.

Hypothesis 2. It is hypothesized that the presence of ADHD + comorbid aggressive/oppositional behavior (i.e., comorbid disruptive behavior disorders; DBD) will moderate intervention effects. Specifically, it is hypothesized that the DRC intervention will be more effective for children with comorbid DBD because they will have increased classroom/social impairment and therefore more opportunity to exhibit improvement.

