2.0 Scientific Endpoints

2.1 Describe the scientific endpoint(s), the main result or occurrence under study.

*NOTE: Scientific endpoints are outcomes defined before the study begins to determine whether the objectives of the study have been met and to draw conclusions from the data. Include primary and secondary endpoints. Some example endpoints are: reduction of symptoms, improvement in quality of life, or survival. Your response should **not** be a date.*

Response:

Primary scientific endpoints are blinded observations of classroom behavior collected at the end of the school year and teacher ratings on the Disruptive Behavior Disorders Rating Scale, Impairment Rating Scale, Academic Performance Rating Scale, and BASC-2 rating scale. Teachers will also complete a rating of IEP goal attainment at the end of the school year.

Secondary outcome measures include assessments of academic achievement, classroom functioning, impairment, parent and teacher satisfaction with treatment, and student-teacher relationship.

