The SBTR has been successfully employed as a primary outcome in our Goal 2 project ([name], Vujnovic et al., 2010; see preliminary study 2), along with two other IES-funded projects, one a between-group study of school-wide social and character development programs ([name], P.I., <http://www.sacdprojects.net>), and the other a study designed to investigate the best dose and sequencing of school-based treatments for children with ADHD ([name], P.I., R324B06045). The SBTR observation system has good inter-rater reliability – the mean difference between the observers on total rule violations recorded was 1.8 (SD=2.3; Range=0-12). For the total rule violations variable, the correlation between the two observers was .96 (p < .001), supporting the inter-rater reliability of the observation measure. The SBTR observation system also demonstrated moderate correlation with the DRC recorded by the teacher (r= -.46), suggesting the half-hour observation relates in the expected manner to the DRC completed over an entire school day ([name], Vujnovic, et al., 2009).

The SBTR observations will occur on three separate days in the month of January (before intervention begins) and three separate days in the month of May for each child. Each observation will last for thirty minutes. Time of day and activity will be controlled. Observers will be blind to the child's treatment condition. To ensure the reliability of this measure, 20% of observations will be completed simultaneously with a second observer to allow the calculation of estimates of reliability. Please see the Table in the Treatment Integrity section below for how these observations are independent and distinct from the integrity observations.

Teacher ratings of behavior. Teachers will be administered the following measures during the first two weeks of the month of January and again in May. The following measures will be used as indicators of student outcomes as secondary measures to the primary observational measure.

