Disruptive Behavior Disorders (DBD) Rating Scale. ADHD, ODD, and CD Diagnostic and Statistical Manual of Mental Disorders (DSM-IV; APA, 2000) symptoms will be measured using the DBD rating scale ([name], Gnagy et al., 1992). The DBD is a 45-item measure that asks parents to rate the DSM symptoms of ADHD, ODD, and CD on a 0-3 point Likert scale (i.e., Not at all, Just a little, Pretty Much, or Very Much). For this study, the average score for the DSM ADHD symptoms will be used as one outcome. The teacher DBD rating scale has good internal consistency (coefficient alpha = .91-.96). Across a number of studies the DBD has also shown sensitivity to behavioral treatment effects ([name], [name], & Massetti, 2005).

Strengths and Difficulties Questionnaire (SDQ): In order to obtain information about the child's functioning across inattentive/hyperactive, emotional symptoms, peer problems, conduct problems, and prosocial

behavior, the SDQ will be administered at intake and during the pre-post assessments during the subsequent academic year. There is an SDQ for parents and teachers, and there is a version for 4-10 year olds and 11-17 year olds (all versions are attached in CLICK).

Domain-Specific Improvement Rating. At the endpoint assessment, teachers will complete impressions of improvement on each of the child's academic and socially related behaviors (Guy, 1976; [name] et al., 2000). This measure will ask teachers to rate improvement on each goal/objective at the end of the school year on a seven-point Likert scale (Very much worse to Very much improved; the midpoint indicates No change). Thus, scores can range from 1.0-7.0. Scores will be averaged across items to provide an overall index of improvement at post-treatment. Ratings of improvement have long been used in numerous pharmacological and behavioral treatment studies. This scale has been shown to be sensitive to behavioral treatment effects in Summer Treatment Program classrooms ([name] & Hoza, 1996; [name] et al, 2000), parent training interventions ([name], Chacko, et al., 2009), our Goal 2 Study ([name], Vujnovic, [name], et al., 2010), and a randomized trial of a school-wide behavioral intervention ([name], Massetti, et al., 2007). The global improvement rating has demonstrated inter-rater reliability (e.g., Tolin et al., 2007; $r = .81$), and clinician-rated improvement scores correlate with parent reports of improvement for individualized target behaviors (Arnold et al., 2003).

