At the endpoint assessment, teachers will complete impressions of improvement on each of the child's academic and socially related IEP goals and objectives with those unrelated to social or academic outcomes, such as fine motor or speech goals, removed (Guy, 1976; [name] et al., 2000). This measure will ask teachers to rate improvement on each goal/objective at the end of the school year on a seven-point Likert scale (Very much worse to Very much improved; the midpoint indicates No change). Thus, scores can range from 1.0-7.0. Scores will be averaged across items to provide an overall index of improvement at post-treatment. Ratings of improvement have long been used in numerous pharmacological and behavioral treatment studies. This scale has been shown to be sensitive to behavioral treatment effects in Summer Treatment Program classrooms ([name] & Hoza, 1996; [name] et al, 2000), parent training interventions ([name], Chacko, et al., 2009), our Goal 2 Study ([name], Vujnovic, et al., 2010), and a randomized trial of a school-wide behavioral intervention ([name], Massetti, et al., 2007). The global improvement rating has demonstrated inter-rater reliability (e.g., Tolin et al., 2007; $r = .81$), and clinician-rated improvement scores correlate with parent reports of improvement for individualized target behaviors (Arnold et al., 2003).

Primary Measures of Academic Functioning.

Academic Performance Rating Scale (APRS). The APRS is a 22-item measure that asks teachers to rate different aspects of a child's academic performance in the classroom (DuPaul, Rapport, & Perriello, 1991). The APRS (DuPaul et al., 1991) includes an Academic Productivity factor (7 items) that relates to work completion and accuracy, independent work, and following directions (coefficient alpha = .94; test-retest reliability over two weeks = .93), an Academic Success (12 items) factor related to the child's academic achievement, recall, and ability (coefficient alpha = .95; test-retest reliability over two weeks = .91).

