Specifically, each outcome score will be regressed on the corresponding pre-test score, a treatment indicator, and four covariates (medication status, grade level, comorbid DBD, and child gender)—the first three of which will be evaluated as potential moderators of treatment in Aim 2. Although the pretest score can be conceived as simply another covariate, it is distinguished here to emphasize the point that its inclusion results in improved statistical power relative to a repeated measures approach for evaluating treatment efficacy (Van Breukelen, 2006). Group differences on adjusted post-test scores (i.e., the significance test of γ_2) will inform the efficacy of using the DRC to enhance academic performance and behavioral outcomes beyond that associated with the routine use of IEP. Measures of primary outcome will be observations of classroom behavior and teacher ratings of academic performance. Measures of secondary outcome will include teacher ratings of symptoms and impairment related to ADHD.

Aim 2. Investigate moderators of treatment outcome.

Aim 2 will be evaluated by extending the ANCOVA model from Aim 1 as follows

$$\gamma_{post}$$

[figure not shown]
$$= \gamma_1 pretest + \gamma_2 DRC + \sum_{j=1}^2 \gamma_j covs \\ + \sum_{k=1}^3 \gamma_k moderator + \gamma_k moderator * DRC + e_i$$

Specifically, Aim 2 will extend the models estimated from Aim 1 by including three additional terms (i.e., the product of each of the three moderators—age group, comorbid DBD, IEP Quality—with the indicator of treatment). Tests of each of these three terms (i.e., $\gamma_{k1}, \gamma_{k2}, \gamma_{k3}$) will inform Aim 2. Each DRC X moderator term that is statistically significant will be probed using simple main effects (i.e., comparisons between DRC and SAU outcomes within each level of the moderator variable) in order to delineate the differential magnitude of treatment on adjusted post-test scores as a function of a given covariate (i.e., primary vs. secondary grade; ADHD only vs. ADHD+DBD; High Quality vs. Low Quality IEP).

Aim 3. Investigate mediators of treatment outcome. Aim 3 will be evaluated using a path analytic approach for testing mediation. The path model will extend the ANCOVA models above by simultaneously

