Response: We relied on our previous ($N = 63$), randomized study contrasting DRC and SAU conditions in order to compute effect sizes for the proposed study (see Preliminary Study 2). Results from that study indicated an effect size of approximately Cohen $d = .50$ (or larger) across the majority of outcomes considered. The weighted random effects effect size of between groups studies for ADHD such as this one was $.74$; thus we are using a conservative effect size relative to the larger literature ([name] et al., 2009). We also assumed that covariates (most prominently the pre-test score) would explain at least 45% of the observed variation in post-test scores (in the Goal 2 study using comparable covariates 47% of the variance for post-test scores for objective observations and teacher ratings of ADHD was explained by pre-test scores).

Given these assumptions, Aim 1 will have power of $.80$ to detect effects of Cohen $d = .50$ with $N = 71$ participants. In order to estimate power for Aim 2, we assumed treatment effects of Cohen $d = .4$ and $.6$ within moderator groups (e.g., the treatment effect would be Cohen $d = .4$ in intermediate grades compared to Cohen $d = .6$ in primary grades), which, given the sampling plan that balances participants across levels of dichotomous moderators, is consistent with the marginal treatment effect of Cohen $d = .50$ used for Aim 1. In order to detect treatment effects as small as Cohen $d = .40$ (given $R^2 = .45$, as per Aim 1) with power of $.80$, $N = 105$ participants are necessary. Hence, the total sample size needed to power Aim 2 at $.80$ is adequate at $N = 216$ (i.e., 108 participants $\times 2$ levels of moderator). Based on recent work by Fritz and MacKinnon (2007), the proposed total sample size of 216 will provide power of greater than $.80$ to detect moderate sized indirect (mediated) effects (there is no standard metric for reporting effect sizes for indirect effects). We

conclude that N=216 participants results in power of .80 or greater to address all three motivating aims. The use of modern methods for dealing with missing data (Multiple Imputation for Aims 1 and 2, Full Information Maximum Likelihood estimation for Aim 3) ensure that all N = 216 participants will contribute to each analysis.

17.3 Describe any procedures that will be used for quality control of collected data.

Response:

Treatment Integrity and Fidelity of the Consultant Activities

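### The two teacher improvement ratings are collected only at endpoint, so the planned ANCOVA has no pre-test to use for them and the R² of .45 behind the power statements does not carry over

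*Combined protocol and SAP*

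**What the plan says.** Section 17.1 (Aim 1) gives one model for all outcomes: "each outcome score will be regressed on the corresponding pre-test score, a treatment indicator, and four covariates". The four covariates are medication status, grade level, comorbid DBD and gender. No alternative is given for an outcome without a baseline.

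Section 10.2, under Rating of IEP Goals, describes a rating of change: "At the endpoint assessment, teachers will complete impressions of improvement on each of the child's academic and socially related IEP goals and objectives". It uses a seven-point scale from much worse to much improved, with no change at the midpoint. "Scores will be averaged across items to provide an overall index of improvement at post-treatment". The Domain-Specific Improvement Rating in the same section has the same timing, scale and scoring.

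Three other passages bear on the point:

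- **Status of the outcome.** Section 1.2, Hypothesis 1: "Children who have a DRC will also demonstrate better outcomes on measures of IEP goal attainment, school functioning, and academic progress". Section 2.1, in the paragraph on primary endpoints: "Teachers will also complete a rating of IEP goal attainment at the end of the school year".
- **General timing.** The lead-in to the teacher ratings in section 10.2 says: "Teachers will be administered the following measures during the first two weeks of the month of January and again in May". Both improvement ratings fall in the list that follows.
- **A separate measure.** Also under Rating of IEP Goals, teachers rate goal attainment on the DRC or ITBC over three days at baseline and again at endpoint.

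Section 17.2 states: "We also assumed that covariates (most prominently the pre-test score) would explain at least 45% of the observed variation in post-test scores". Its support is a figure of 47% from the Goal 2 study, for observations and teacher ADHD ratings. From R² = .45 it derives N = 71 for Aim 1 (d = .50) and N = 105 for a moderator level in Aim 2 (d = .40), and it concludes that 216 gives power of at least .80 for all three aims.

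**The concern.** A rating of improvement since January cannot be given in January. For these two outcomes the pre-test term is therefore undefined, and the analyst must either drop it or choose a substitute. Several January teacher scores could serve (IRS, APRS, DBD, DRC/ITBC). If the choice is not fixed beforehand, it may be made after the data are seen, for a measure that section 2.1 may count among its main endpoints.

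If the term is dropped, comorbid DBD is the only remaining covariate that reflects severity, although how far a child can improve depends on January functioning. The precision promised in section 17.2 is then not available for these outcomes, and its power statements do not describe them.

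**Working it through.** **Inputs**

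- d = .50, power .80, R² = .45, N = 71 (section 17.2, Aim 1).
- d = .40, N = 105 needed, 108 per moderator level planned (section 17.2, Aim 2).
- Equal allocation, 108 per group, 216 in total (section 4.1).
- Alpha is not stated. Two-sided .05 is assumed.
- R² without a pre-test is not given. A range of 0 to .10 from the four remaining covariates is assumed.

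**Formulas**

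- Normal approximation: total N = 4(1 − R²)(1.960 + 0.842)²/d², rounded up to equal arms.
- Noncentral t: noncentrality = d/√(1 − R²) × √(N/4).
- Standard error relative to plan: √((1 − R²)/.55).

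**Step 1: reproduce the plan.** For d = .50 and R² = .45, 4 × .55 × 7.849/.25 = 69.1, so 70 by the normal formula. The t calculation gives 72, with power .7996 at N = 71. The stated 71 reproduces. One-sided .05 gives 56 and does not. For d = .40, 4 × .55 × 7.849/.16 = 107.9, so 108 (110 by t), within 3% of the stated 105 by the normal formula.

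**Step 2: remove the pre-test.** The first two N columns are total N for d = .50 and power .80. Power is from the t calculation.

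| R² | SE ratio | N, normal | N, t | Power, N = 71, d = .50 | Power, N = 216, d = .50 | Power, N = 108, d = .40 |
|---|---|---|---|---|---|---|
| .45 (plan) | 1.00 | 70 | 72 | .80 | .999 | .79 |
| .10 | 1.28 | 114 | 116 | .59 | .971 | .58 |
| .05 | 1.31 | 120 | 122 | .57 | .964 | .56 |
| 0 | 1.35 | 126 | 128 | .55 | .955 | .54 |

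For example, at R² = 0 the standard-error ratio is √(1/.55) = 1.35.

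**Step 3: what a January proxy could recover.** If a January teacher score raised R² to between .09 and .25 (assumed), the standard-error ratio would be √(.91/.55) = 1.29 to √(.75/.55) = 1.17, and the N needed for Aim 1 would be 118 to 98.

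**The case against.** The strongest reply is that IEP goal attainment does have a baseline. The DRC/ITBC teacher ratings are taken in January and May and fit the stated model, and Hypothesis 1 speaks of measures in the plural. This stands. A reader might infer that an outcome of Hypothesis 1 cannot be analysed at all. The documents do not support that: one measure of the construct lacks a pre-test and another has one. Section 2.1 does not say which it means.

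Second, section 17.1 itself treats the pre-test as one covariate among others, and under randomization leaving it out does not bias the comparison. This also stands. The cost is precision, and chance imbalance in January severity is already part of the standard error. Nor is all adjustment for severity lost, because comorbid DBD stays in the model and section 1.2 treats it as a marker of impairment and room to improve.

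Third, 71 is not the trial's sample size. A reader might infer that Aim 1 is underpowered. It is not, at about .96 with 216.

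Fourth, the lead-in in section 10.2 gives January and May for the listed teacher measures, and section 10.3 refers to an administration schedule that is not among the documents reviewed. The specific text for both ratings says endpoint, and a change score before treatment would have no meaning, so the specific text is the better reading. The two statements still need to be reconciled.

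**Conclusion.** The point holds for the two improvement ratings only. The Aim 1 model cannot be fitted to them as written, and R² = .45 has no stated support for them. The effect on Aim 1 is a loss of precision (standard error about 1.28 to 1.35 times that planned), with ample power left at N = 216. The larger effect is on Aim 2: by the plan's own within-level method, power for these outcomes at N = 108 and d = .40 is about .54 to .58. The conclusion in section 17.2 that all three aims have power of .80 or more therefore does not extend to them.

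These figures assume two-sided .05 and an R² of 0 to .10 without a pre-test. If the four covariates explain more than that, the loss is smaller.

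**What to change.** **Section 17.1.** State that for the two endpoint-only improvement ratings the pre-test is replaced by one named January teacher score: either the DRC/ITBC goal-attainment rating or the IRS/APRS score. The DRC/ITBC rating is closest in content. If it is chosen, confirm that it is obtained before randomization, because section 10.1 builds the DRC targets in consultations that follow assignment. The same provision could cover the parent and teacher satisfaction measure, which is also collected only at the end of school.

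**Section 10.2.** Reconcile the general January-and-May statement with the endpoint-only text for the two ratings. In section 2.1, say which rating of IEP goal attainment is meant.

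**Section 17.2.** Limit the R² = .45 statements (N = 71 and N = 105) to outcomes measured in both January and May. For the improvement ratings, state that with an assumed R² of 0 to .10 Aim 1 needs about 114 to 128 in total, that power at 216 is about .96, and that within-level power at N = 108 and d = .40 is about .54 to .58.

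**Cost.** A few sentences, and less favourable stated power for these outcomes. The IRS, APRS and DRC/ITBC scores are already planned, so no new measure is needed and the sample size does not change.

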IEP Quality. IEP quality will be assessed using a composite rating by study investigators. Prior to quality ratings, IEPs will be de-identified to remove the participant name and information as well as any information about the school or district. Ratings will evaluate the alignment between needs listed in the IEP with goals/objectives stated in the IEP. This will be one way to determine the quality of the IEP document itself – well-written IEPs should have IEPs with close alignment between academic, behavior, and social/emotional needs and the goals to realize improvement (see appendix C for an outline of the coding sheet to be used in the present study; Pariseau, 2011). We will also track which goals are added by consultants to the DRC that were noted as needs by the teacher, but not listed on the IEP. The occurrence of these issues may indicate that the IEP is outdated, poorly constructed, or not reflective of current behavior. These indicators will comprise an IEP quality score investigated as a moderator. Specifically, the score will be calculated as: (Alignment between needs and goals + additional targets added)/overall alignment). A score of 1 would indicate perfect alignment whereas a score below 1 would indicate discrepancy between needs and goals.

Mediators

Three key components of the DRC intervention that are central to our logic model (see figure in the introduction) will be investigated as mediators of treatment outcome. It is expected that relative to the SAU group, the children in the DRC condition will experience a more positive classroom environment, receive more consistent feedback from teachers, and experience more consistent home-based consequences for school behavior. These three variables will each have a partial mediating effect, and the sum total will fully mediate the effect on treatment outcome.

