17.0 Data Management and Analysis

17.1 Describe the data analysis plan, including any statistical procedures. This section applies to both quantitative and qualitative analysis.

Response: To ensure appropriate manipulation of the independent variable the treatment integrity data described above will be collected and analyzed. The distributional characteristics of all dependent variables will be examined. If outcomes are appreciably non-normal, we will consider power transformations where appropriate. Although we expect that our cross-site and cross-cohort training efforts will mitigate the possibility of any site, cohort, or consultant differences, we will still conduct sensitivity analyses that evaluate treatment effects separately by cohort, site, and

consultant. As the study is powered for efficacy analyses and we do not anticipate being powered to detect cohort/site/consultant effects, these analyses will emphasize effect size comparisons. To the extent that any differences are revealed, we will improve cross-site and cross-cohort training and fidelity observations, as well as to consider the inclusion of site, cohort, or consultant as additional covariates. Benjamini-Hochberg adjustments will be used throughout in order to control for the false discovery rate associated with multiple comparisons across outcomes (Benjamini & Hochberg, 1995). This strategy is implemented in SAS® using PROC MULTTEST. Multiple imputation methods will be used to accommodate missing data (Allison, 2002). This strategy is implemented in SAS® using PROC MI and MIANALYZE.

Aim 1. Investigate the effectiveness of using a DRC to link the child with ADHD's IEP to daily classroom behavior.

Aim 1 will be evaluated using Analysis of Covariance (ANCOVA) models of the following form

$$y_{post} = \gamma_1 \text{pretest} + \gamma_2 \text{DRC} + \sum_{j=1}^5 \gamma_j \text{covariates} + e_i$$

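### Section 17.1 gives conflicting covariate and moderator lists for Aims 1 and 2, and the IEP quality score that would reconcile the equations is partly built after randomisation

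*Combined protocol and SAP*

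**What the plan says.** **Aim 1 (section 17.1).** The text regresses each post-test score on its pre-test, a treatment indicator and "four covariates (medication status, grade level, comorbid DBD, and child gender". It then says of these covariates: "the first three of which will be evaluated as potential moderators of treatment in Aim 2". The displayed equation writes the pre-test and DRC as separate terms and sums covariates from 1 to 5.

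**Aim 2 (section 17.1).** The text says "Aim 2 will extend the models estimated from Aim 1 by including three additional terms" and defines those terms as "the product of each of the three moderators—age group, comorbid DBD, IEP Quality—with the indicator of treatment". The displayed equation has two covariates and, for each of three moderators, a main effect plus its product with DRC.

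**IEP quality (section 10.2).** The score combines the alignment of needs and goals in the IEP with additional targets. For the latter, the study will "track which goals are added by consultants to the DRC" where the teacher noted a need that the IEP does not list.

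**Medication.** Sections 4.1 and 10.1 call medication a potential moderator when describing stratification. The hypotheses (1.2), the background (3.1) and the moderator measures (10.2) give only grade, comorbidity and IEP quality.

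**The concern.** Aim 1 is the efficacy analysis and Aim 2 carries three named hypotheses, so each needs one identifiable model. As written, an analyst must decide three things: how many covariates enter Aim 1 and which they are, whether IEP quality has a main effect in Aim 2, and whether medication x DRC is a planned test. Each could be decided after results are seen.

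The choice on IEP quality matters most. If the score depends on what consultants do after assignment, then adjusting the Aim 1 effect for it conditions on something treatment may have changed. Using it as the Aim 2 moderator has a related fault: DRC and SAU children at the same score level may have reached it by different routes, so the within-level comparison is no longer a purely randomised one. Aim 3 inherits the question, because its covariates include the moderators.

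**Working it through.** **1. The statements side by side (section 17.1)**

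| Place | Covariates besides pre-test and DRC | Moderators | Terms added in Aim 2 |
|---|---|---|---|
| Aim 1 text | 4: medication, grade, DBD, gender | medication, grade, DBD | – |
| Aim 1 equation | 5, unnamed | – | – |
| Aim 2 text | as in Aim 1 | age group, DBD, IEP quality | 3 products |
| Aim 2 equation | 2, plus 3 moderator main effects | 3, unnamed | 3 products |

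With the Aim 2 moderators taken as grade, DBD and IEP quality, the two remaining covariates are medication and gender. Then 2 + 3 = 5, which is the Aim 1 equation count, but only if IEP quality is in the Aim 1 model. The Aim 1 text leaves it out.

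**2. When the IEP quality score is formed**

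Section 10.1 gives the order: baseline measures, random assignment, consultant assignment, then consultant visits at which targets not on the IEP are identified. Added targets therefore come after randomisation. In SAU, a goal list is made but is not used to develop a DRC, so goals added to the DRC have no exact SAU counterpart, and the plan does not say what replaces them.

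If the score differs between arms by D SD because of assignment, and relates to the outcome by b per SD within arms, least squares gives: adjusted effect = unadjusted effect − b × D. The documents give neither b nor D, so the shift cannot be sized.

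**3. What a missing main effect would do**

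The plan states no figure for this. Inputs from the plan are N = 216 with 108 per arm (10.1) and covariate R² = .45 (17.2), so residual variance is 1 − .45 = .55. As a check on that input, with two-sided 5% alpha (assumed) and 80% power, total N = 4 × .55 × (1.960 + .842)² / d². This gives 69.1, so 70, at d = .50 (plan: 71) and 107.9, so 108, at d = .40 (plan: 105). The input is close to what the plan used.

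Assume IEP quality is split evenly into two levels, there is no true moderation, treatment is coded 0/1 and the IEP quality main effect is left out. The product is then non-zero only in the DRC arm, and its coefficient estimates the whole IEP quality effect b. Its standard error is about √.55 × √(4/108) = .742 × .192 = .143. The rejection rate is Φ(b/.143 − 1.96) + Φ(−b/.143 − 1.96). Two simulations of 4,000 trials per setting agree with this; the last two columns come from one of them.

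| b (SD, assumed) | Formula | Simulated, 0/1 coding, no main effect | ±0.5 coding, no main effect | Displayed equation |
|---|---|---|---|---|
| .1 | 11% | 10.2%, 11.9% | 5.4% | 5.5% |
| .2 | 29% | 27.9%, 28.0% | 4.7% | 5.0% |
| .3 | 56% | 53.7%, 54.3% | 4.9% | 5.4% |
| .4 | 80% | 76.6%, 78.7% | 4.3% | 5.1% |

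At b = 0 the 0/1 rate without the main effect is 5.3%. With a continuous score the 0/1 rates are higher (26.1%, 73.8% and 97.2% at .1, .2 and .3 per SD), and ±0.5 coding gives 5.1% to 7.9% over 0 to .5. All are single-test rates, before the Benjamini-Hochberg adjustment.

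**The case against.** The strongest reply is that the displayed Aim 2 equation already contains the main effects, and the paragraph after it names IEP quality among the moderators. A reader might infer that the plan specifies an interaction without its main effect and will produce false moderation. The documents do not support that. The faulty model appears only if the equation is set aside and the Aim 2 sentence is joined to the four-item Aim 1 list. Even then it needs 0/1 coding, which the plan does not state, and an IEP quality association, for which the plan gives no figure.

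A reader might also infer that every reading does harm. That does not follow either. Four covariates in Aim 1, with the IEP quality main effect and product entering in Aim 2, avoids both the missing main effect and the adjustment of the primary model. The five may be a counting slip, or may include the pre-test, which section 17.1 says can be viewed as another covariate, although the equation already shows it separately.

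On medication, no hypothesis is stated and four places give the same moderator list without it, so the intended tests are fairly clear.

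What stands is that the text and equations conflict, that the harmless reading is nowhere stated, and that none of these replies addresses the timing of the IEP quality score.

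**Conclusion.** The point holds as a specification conflict with one substantive consequence. The covariate counts (four against five), the moderator lists (medication against IEP quality) and the Aim 2 additions (products only, against main effects plus products) disagree on the page. The reading under which the equations match puts IEP quality into the primary efficacy model, and that score has a component formed after randomisation. The same component affects Aim 2 under any version of the model. The size of this bias is unknown.

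The false-positive rates (about 10–12%, 28%, 54% and 77–79% for assumed effects of .1, .2, .3 and .4 SD) are a hypothetical cost of following the sentence over the equation with 0/1 coding, and are not a prediction for this trial. Under the displayed equation, or with ±0.5 coding and a two-level moderator, the rate is about 5%. This should be settled before any outcome is analysed by group.

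**What to change.** - **Aim 1:** set the sum to the four named baseline covariates, plus the pre-test, and state that IEP quality is not in this model.
- **Aim 2:** state that the model adds the IEP quality main effect and three products (grade, DBD and IEP quality with DRC), as its equation shows.
- **IEP quality:** compute the moderator from the pre-randomisation IEP only, using the alignment of needs and goals. Report consultant-added targets separately.
- **Medication:** delete the Aim 1 clause that makes the first three covariates the moderators. Keep medication as a covariate and label any medication x DRC test exploratory.
- **Aim 3:** carry the same covariate list and IEP quality definition into the path model.

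Most of this is rewording of section 17.1 and needs no new data. The one real cost is in section 10.2: the scoring formula changes and one planned component of the IEP quality score is dropped from the moderator.
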